#### **6.1.3 Post-Treatment Follow-Up Period**

##### **6.1.3.1 End of Study: 4 weeks ( $\pm$ 7 days) after EOT or ET**

- Laboratory tests:
  - Complete blood count with WBC differential
  - Serum chemistry
  - Lipid panel (fasting whenever possible)
  - Serum iron, ferritin, TIBC, TSAT
  - CHr
  - HbA1c
  - Reticulocyte count
  - Special laboratory analytes
  - Archival serum/plasma samples (optional donation, separate consent form)
- Targeted physical exam
- Serum hCG test for women of childbearing potential

- Blood pressure, HR
- Adverse event recording
- Concomitant medication recording
- Procedures and nondrug therapy recording

### **6.1.3.2 Subject Discontinuation**

Subjects may discontinue from the study at any time. Discontinued subjects should be encouraged to complete the ET and the EOS visit procedures. The appropriate documentation must be entered on the CRF. Subjects should be discontinued from the study for any of the following reasons:

- Subject no longer consents to participate in the study
- Investigator's decision that it is in the best interest of the subject to be withdrawn from the study
- Adverse events
- Significant noncompliance with study procedures, as determined by the Investigator or Sponsor
- Lack of Efficacy / Meets ESA withdrawal criteria (for subjects on roxadustat; see also [Section 3.6.3.2](#))
- Subject is lost to follow-up
- Subject is no longer requiring dialysis due to kidney transplant
- Pregnancy
- Death
- Site terminated by Sponsor

Women of childbearing potential who withdraw from this study will continue contraception for 12 weeks following the last study drug administration. Male subjects with partners of childbearing potential must agree to use a medically acceptable method of contraception during the study and for 12 weeks following the last study drug administration.

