#### 3.6.3.2 Erythropoiesis Stimulating Agents (Roxadustat Arm Only):

The use of ESAs is not permitted during the Treatment Period, except if all of the following criteria are met:

- A subject's Hb level has not responded adequately despite two or more consecutive roxadustat dose increases or the roxadustat dose has reached the maximum dose limit
- Other causes for lack of response or declining Hb, such as iron deficiency, bleeding, acute inflammatory conditions, have been ruled out
- Reducing risk of alloimmunization in transplant eligible patients is a goal.

Roxadustat and ESA may not be co-administered. Treatment with an approved ESA may be initiated  $\geq$  3 days after the last roxadustat dose.

If the situation permits, the Investigator should inform the Medical Monitor prior to initiation of ESA therapy.

Subjects may receive **one course** of ESA rescue during the Treatment Period.

Erythropoiesis-stimulating agent rescue should stop after 4 weeks or once Hb exceeds 9 g/dL, whichever occurs first. If a subject requires more than 4 weeks of ESA rescue therapy due to inadequate Hb response, the Medical Monitor should be contacted.

Treatment with roxadustat may resume after the following intervals:

- Two days after stopping epoetin alfa
- One week after stopping darbepoetin alfa
- Two weeks after stopping methoxy polyethylene glycol-epoetin beta (Mircera®)

If more than one course of ESA rescue is required during the Treatment Period, the subject must be discontinued permanently from the study, and is considered a Treatment Failure.

Inadvertent ESA administration including ESA administration by hospital staff in Roxadustat subjects should not be counted as rescue unless above criteria are met; these subjects may be allowed to continue on study, if considered safe by the Investigator and Medical Monitor.

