#### **6.1.2.6 Early Termination (ET)**

If a subject discontinues study medication permanently during the Treatment Period, perform the EOT assessments at the time of withdrawal from dosing or as soon as possible ([Section 6.1.2.5](#)). Erythropoiesis-stimulating agents may be started  $\geq$  3 days after the last dose of roxadustat.

Unless consent is withdrawn, these subjects will be followed up for CV events of interest, vital status, and hospitalization until study closure.

These subjects will be followed up every 3 to 6 months (depending on the availability of the subjects) until study closure. These visits may occur either in person or via telephone.

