## 7.4 Safety Assessments and Endpoints

Study-specific safety will be assessed by evaluating the following:

- TEAEs, TESAEs, and clinically significant laboratory values from baseline
- Vital signs, ECG findings and clinical laboratory values

Safety interpretation will also be made based on analyses of composite endpoints derived from adjudicated events pooled across multiple studies in the roxadustat Phase 3 program. The members of an independent adjudication committee blinded to treatment assignment will adjudicate the following events in multiple phase 3 studies:

- Death from any cause, MI, stroke, congestive heart failure requiring hospitalization, unstable angina requiring hospitalization, hypertensive emergency, deep venous thrombosis, pulmonary embolism, and vascular access thrombosis.
- Various region-specific pooled analyses of composites of these adjudicated events, pooled across multiple studies will be conducted. The analyses of the adjudicated events will be detailed in the region-specific pooled SAPs.

**For US (FDA) Only:** The primary safety endpoint in this study is the Major Adverse Cardiac Event (MACE) composite endpoint, defined as time to first occurrence of death from all causes, MI, or stroke, for the purpose of being pooled across multiple similar studies in the Phase 3 program. None of the individual studies are powered to meet the MACE primary safety endpoint individually. The pooled MACE analysis is only for purposes of supporting a US FDA regulatory filing of roxadustat.

The above adjudicated safety events may also be used to support the pooled analyses of additional composite safety endpoints across multiple studies in the Phase 3 program, such as MACE+ (death, MI, stroke, congestive heart failure requiring hospitalization, and unstable angina requiring hospitalization), or a composite which consists of all of the adjudicated events.

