#### **9.3.5.2 Deaths**

For any death occurring during the subject's study participation, regardless of attribution, the Investigator will report the death immediately to the Sponsor's Medical Monitor and their designated safety management vendor.

The Investigator should notify Sponsor and their designated safety management vendor of any death or other SAE occurring after a subject has discontinued or terminated study participation that may reasonably be related to the study.

The Investigator must submit the SAE Report Form and complete the appropriate CRF page for the event that led to the subject's death.

When reporting a death, the event or condition that caused or contributed to the fatal outcome should be recorded as the primary event term on the SAE Report Form.

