- k All assessments should be done prior to first study drug administration.
- l Dispense every other week
- m Subjects who prematurely discontinue study treatment will complete the ET and EOS visits, and – unless consent is withdrawn – will continue to be followed for CV events of interest, vital status and hospitalizations until study closure. These subjects will be asked to return for study visits every 3 to 6 months, or be available via telephone.

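### Protocol sections 6.1.3.2 and 3.6.3.2 discontinue subjects from the study for reasons that section 6.1.2.6 treats as stopping drug only, so MACE follow-up to closure depends on which section a site applies

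*Protocol*

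**What the plan says.** Two sets of instructions apply to a subject who stops early.

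**Follow to closure.** Protocol section 6.1.2.6 is triggered when study medication is permanently stopped: "Unless consent is withdrawn, these subjects will be followed up for CV events of interest, vital status, and hospitalization until study closure". Contacts are every 3 to 6 months, in person or by telephone. Footnote m of Protocol Appendix 3, repeated in SAP Appendix 1, says that such subjects complete the ET and EOS visits and "will continue to be followed for CV events of interest, vital status and hospitalizations until study closure", again unless consent is withdrawn.

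**Leave the study.** Protocol section 6.1.3.2 opens its list with "Subjects should be discontinued from the study for any of the following reasons". Its ten reasons include adverse events, significant noncompliance, pregnancy, "Subject is no longer requiring dialysis due to kidney transplant" and the bullet beginning "Lack of Efficacy / Meets ESA withdrawal criteria (for subjects on roxadustat; see also". They stand in one list with withdrawn consent, loss to follow-up and death. The section encourages the ET and EOS visits and does not refer to 6.1.2.6. Section 3.6.3.2, and the same text in the synopsis, says that after a need for more than one ESA rescue course "the subject must be discontinued permanently from the study, and is considered a Treatment Failure". That rule is for the roxadustat arm only.

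**Reporting of deaths.** Section 9.3.5.2 requires every death during study participation to be reported whatever its attribution. Afterwards it asks only for "any death or other SAE occurring after a subject has discontinued or terminated study participation that may reasonably be related to the study". Under section 9.3.1 general AE and SAE reporting ends 28 days after the ET/EOT visit.

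**Endpoint.** Section 7.4 names MACE as the US primary safety endpoint, "defined as time to first occurrence of death from all causes, MI, or stroke", to be pooled across Phase 3 studies. It adds that no single study is powered for it.

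**The concern.** The US safety comparison counts deaths from any cause, MI and stroke over time. Stopping study drug should not end observation for it, and section 6.1.2.6 says that it does not. Yet sections 6.1.3.2 and 3.6.3.2 describe the same stops as leaving the study, and under section 9.3.5.2 that label changes which later deaths the sponsor must be told about.

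If some sites act on the label, follow-up is cut short for reasons that may be related to prognosis, such as adverse events or non-response. One route out of the study also exists in the roxadustat arm alone, in an open-label trial. The lost period could be long: section 6.1.2 sets a common closeout driven by programme-wide event counts, and section 3.1 allows treatment to run up to about 3 years after the last subject is randomized.

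**Working it through.** The documents give no discontinuation rate, MACE rate, hazard ratio, safety margin or event target, so there is no planned figure to reproduce. The main check is a comparison of the passages.

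**1. Trace three subjects through the text.**

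| Reason for stopping | Sections 6.1.3.2 / 3.6.3.2 | Section 6.1.2.6 and footnote m |
|---|---|---|
| Adverse event | Discontinue from the study; ET and EOS visits encouraged | Study drug stopped, consent not withdrawn: follow to closure |
| Kidney transplant | Same | Same |
| Second ESA course (roxadustat) | Must leave the study permanently | Same |

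In each row both instructions apply. The only exception in 6.1.2.6 is withdrawn consent; in 6.1.3.2 withdrawn consent is one of ten reasons. No section ranks one rule above the other.

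**2. Follow the label into death reporting.** If the subject is treated as having left the study, the last planned contact is the EOS visit, 4 weeks (± 7 days) after ET. An unrelated death after that falls outside 9.3.1 and outside the relatedness condition in 9.3.5.2, although it is a MACE event. If the subject is treated as being under 6.1.2.6, vital-status follow-up should find the death.

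**3. Check symmetry.** The second-course rule and the ESA criterion in the lack-of-efficacy bullet are limited to roxadustat. The epoetin alfa arm has no matching rule.

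**4. Illustrate what unequal loss could do. Every input here is assumed.** Let g be the share of person-time after discontinuation, k the event rate after discontinuation relative to before, and l the fraction of post-discontinuation time not followed in the roxadustat arm. Epoetin follow-up is complete and the true rate ratio is 1.

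Observed relative rate, roxadustat = [(1 − g) + g(1 − l)k] / [(1 − g) + g(1 − l)]

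Relative rate, epoetin = (1 − g) + gk

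With g = 0.20, k = 2 and l = 0.50, roxadustat is (0.80 + 0.20)/0.90 = 1.111, epoetin is 0.80 + 0.40 = 1.20, and the apparent ratio is 1.111/1.20 = 0.93. Other cases with g = 0.20:

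| k | l = 0.10 | l = 0.25 | l = 0.50 |
|---|---|---|---|
| 0.5 | 1.01 | 1.02 | 1.05 |
| 1 | 1.00 | 1.00 | 1.00 |
| 2 | 0.99 | 0.97 | 0.93 |
| 3 | 0.98 | 0.94 | 0.87 |

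For k = 0.5 and l = 0.50 the working is (0.80 + 0.05)/0.90 = 0.944, divided by 0.80 + 0.10 = 0.90, which gives 1.05. The direction therefore depends on k, which the documents do not supply. With equal rates there is no bias.

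**The case against.** The best defence is that 6.1.2.6 already settles the matter. Anyone removed from the study has also stopped study medication, so the trigger is met, and only withdrawn consent lifts the requirement. Footnote m puts the ET and EOS visits and the continued follow-up in one sentence, and SAP Table 9 defines the EOS window as excluding long-term follow-up after early termination. Section 6.1.3.2 is silent on that follow-up and does not forbid it. Because its list contains death and loss to follow-up, it can also be read as a list of disposition reasons. Section 9.3.5.2 governs notification to the sponsor and safety vendor, whereas all-cause deaths off drug are meant to come from vital-status follow-up.

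Much of this stands. Follow-up to closure is probably what the sponsor intends, and a site that stopped at EOS would breach 6.1.2.6 and footnote m. But to read the protocol that way a site must set aside the mandatory wording of 3.6.3.2 and the participation test in 9.3.5.2, and nothing tells it to.

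The arm-specific route is also narrow. All three rescue criteria must be met, including a goal of reducing alloimmunization risk in transplant-eligible patients, and inadvertent or hospital ESA does not count as rescue unless they are. That limits how large an arm difference this rule could produce, but does not remove it.

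**Conclusion.** The conflict is in the current text and should be resolved. It puts at risk the ascertainment of MACE, most plainly its all-cause-death component, for subjects who stop drug without withdrawing consent. Loss of follow-up is possible but not certain, could be informative, and could differ by arm.

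A reader might infer three stronger things that the documents do not support:

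- **That the protocol ends follow-up for these subjects.** It does so only if 6.1.2.6 and footnote m are ignored.
- **That the subjects lost are those at highest risk.** This is plausible for adverse events, but no event rates by reason are given. For transplant, the protocol's own background (section 1.1.1) points the other way: an average life expectancy of 16.4 years for a transplant patient against 5.9 on dialysis.
- **That the MACE comparison is biased towards roxadustat.** The illustration shows a shift in either direction, or none, depending on assumed inputs.

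No number of affected subjects can be stated without a discontinuation rate. The consequence also falls on the pooled US analysis. Its analysis plan is a separate document that is not available here, so how off-treatment time is counted or censored is unknown.

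**What to change.** Reconcile the passages without changing any criterion for stopping treatment.

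- **Section 6.1.3.2:** separate discontinuation of study treatment from withdrawal from the study. State that subjects discontinued for any reason other than withdrawn consent, death or loss to follow-up continue follow-up per 6.1.2.6. Set out what happens for subjects at sites terminated by the sponsor and for withdrawals decided by the investigator, since neither fits that rule without an arrangement of its own.
- **Section 3.6.3.2 and the synopsis:** reconcile the second-course wording with 6.1.2.6 by adding that follow-up continues per that section.
- **Section 9.3.5.2:** state that every death during 6.1.2.6 follow-up is reported, regardless of relatedness.

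The cost is a wording amendment and a memo to sites. The contacts every 3 to 6 months are already planned in 6.1.2.6. Whether they are funded cannot be checked, because section 14 places financing in a separate document.

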## **6.2 Missed Visits**

Every attempt should be made to complete all study visits as outlined in the Schedule of Assessments ([Appendix 3](#)). All missed study visits and visits outside the visit window are considered protocol deviations.

### 6.3 Unscheduled Visits

Unscheduled visit(s) and laboratory assessments may be required at the discretion of the Investigator. Please refer to the CRF Completion Guidelines located in the Study Reference Manual for additional information.

### 6.4 Laboratory Assessments

Central laboratory results should be reviewed by the Investigator or another qualified study staff member as soon as it is received. Subject management is dependent upon close review of the laboratory data.

#### 6.4.1 HemoCue® / CritLine®

Hemoglobin values obtained by point-of-care devices such as HemoCue® or CritLine® are used to allow “real-time” dose adjustments for all subjects. HemoCue®/ CritLine® results will be collected in the CRF. Anytime an Hb is obtained via such a point-of-care device, a central lab Hb should be obtained as well, either as part of the regular visit labs, or anytime when a point-of-care Hb is obtained at unscheduled visits, such as during dose-hold for excessive hematopoiesis.

#### 6.4.2 Central Laboratory

All study related tests of blood specimens will be performed by a central laboratory.

Unscheduled and repeat laboratory tests will also be performed by the central laboratory. However, if the turnaround time from the central laboratory is not sufficiently rapid for clinical management of the subject, local laboratory (ie, “stat” labs, USA) test results may be used to make the necessary clinical judgments. In all such cases, a central lab specimen should be obtained at the same time.

A Central Laboratory Manual with instructions on specimen collection, processing, storing, and shipping to the central laboratory will be provided to all participating sites.

Laboratory parameters to be measured in this study are listed in [Table 3](#).

**Table 3      Laboratory Tests**

CBC:	Chemistry Panel:
Basophils	Albumin
Eosinophils	Bicarbonate
Erythrocyte count (RBC)	BUN
Hb	Calcium
Hct	Chloride
Leukocyte count (WBC)	Creatinine
Lymphocytes	Glucose
Mean corpuscular volume	Lipase
Mean corpuscular Hb	Lactate dehydrogenase
Mean corpuscular Hb concentration	Liver Function Tests
Monocytes	ALP
Neutrophils	ALT
Neutrophils, immature (banded)	AST
Platelets	Bilirubin, total and direct
Reticulocyte count	CPK
	GGT
Serum Lipid Panel:	Magnesium
Total Cholesterol	Phosphorus
LDL	Potassium
HDL	Sodium
Triglycerides	Total protein
Serum Iron Profile	Uric acid
Ferritin	HIV and Viral Hepatitis Panel:
Iron	Anti-HCV Ab tests
Reticulocyte Hb content	HBsAg
TIBC	HIV ELISA
TSAT	
Special Laboratory Analytes:	Additional Laboratory Analytes:
Hepcidin	Vitamin B 12
High-sensitivity CRP	Folate
	HbA1c
	Serum β-HCG

**Abbreviations:** ALP = alkaline phosphatase; ALT = alanine aminotransferase; AST = aspartate aminotransferase; BUN = blood urea nitrogen; CBC = complete blood count; CRP = C-reactive protein; ELISA = enzyme-linked immunosorbent assay; GGT = gamma-glutamyl transferase; Hb = hemoglobin; HbA1c = glycated hemoglobin A1c; HBsAg = hepatitis B surface antigen; Hct = hematocrit; HCV = hepatitis C virus; HDL = high-density lipoprotein; HCG = human chorionic gonadotropin; HIV = human immunodeficiency virus; LDL = low-density lipoprotein; RBC = red blood cell; TIBC = total iron binding capacity; TSAT = transferrin saturation; WBC = white blood cell.

**Archival serum/plasma samples:**

A set of serum and plasma samples may be drawn and stored for the future analysis of relevant select biomarkers. Donation of these samples is optional and will be sought through a separate informed consent form (ICF). No genetic testing will be performed for the diagnosis of genetic disorders on these samples.

## 6.5 Electrocardiogram

Local 12-lead ECGs will be performed on all subjects at specific time points as described in the Schedule of Assessments. ECG will be taken after the subject has been lying quietly in the supine position for 5 minutes. Any abnormalities must be evaluated in clinical context (based on subject's medical history and concomitant medication) and the Investigator should determine if it is clinically significant. Clinically significant abnormalities should be reported as an AE. ECG recordings will be kept as source documents. Abnormal ECG findings prior to administration of study drug on Day 1 will be considered baseline conditions.

## 6.6 Renal Ultrasound

A renal ultrasound examination will be performed during screening if no record of a renal imaging modality exists within 12 weeks prior to randomization. Findings of the renal ultrasound to exclude the presence or suspicion of renal cell carcinoma will be required for eligibility. Sites are reminded to schedule the renal ultrasound in a timely manner.

## 6.7 Health Related Quality of Life Questionnaires

All study subjects will be required to complete the following HRQoL questionnaires: SF-36, FACT-An, and EQ-5D-5L.

### 6.7.1 36-Item Short Form Health Survey

The 36-Item Short Form Health Survey is a HRQoL instrument designed to assess generic health concepts relevant across age, disease, and treatment groups. It is aimed at both adults and adolescents ages 18 years and older. The SF-36 consists of 8 domains of health status: physical functioning (PF) (10 items), role physical (4 items), bodily pain (2 items), general health (5 items), vitality (4 items), social functioning (2 items), role emotional (3 items) and mental health (5 items). Two component scores, the Physical Component Scores and the Mental Component Summary can also be calculated. For both the SF-36 domain scores and summary scores, higher scores indicate better health status.

### 6.7.2 FACT-An

The Functional Assessment of Cancer Therapy-General (FACT-G; Version 4) contains 27 items that cover four dimensions of well-being: physical (7 items), functional (7 items), social/family (7 items), and emotional (6 items). A subscale of 13 fatigue specific items plus 7 additional items

related to anemia were developed for use in conjunction with the FACT-G ([Yellen, 1997](#)). The 13 fatigue items plus the 7 additional items related to anemia comprise the Anemia Subscale. Administration of the FACT-G plus the Anemia Subscale is referred to as the FACT-An. The FACT-An has a recall period of the ‘past seven days’. Respondents are asked to provide responses, (ie, ‘Not at all’, ‘A little bit’, ‘Somewhat’, ‘Quite a bit’ and ‘Very much’), to a list of statements which are either positively or negatively phrased. For all FACT-An scales, a higher score indicates better QoL.

### 6.7.3 European Quality of Life Questionnaire in 5 Dimensions

The EQ- 5D-5L consists of the EQ-5D descriptive system and the EQ visual analog scale. The EQ-5D-5L descriptive system comprises 5 dimensions of health: mobility, self-care, usual activities, pain/discomfort, and anxiety/depression. Each dimension has 5 levels: no problems, slight problems, moderate problems, severe problems, extreme problems. The visual analog scale records the respondent's self-rated health status on a graduated (0–100) scale, where the endpoints are labeled ‘Best imaginable health state’ and ‘Worst imaginable health state’ with higher scores for higher HRQoL. EQ-5D-5L health states, defined by the EQ-5D-5L descriptive system, may be converted into a single summary index by applying a formula that essentially attaches values (also called weights) to each of the levels in each dimension.

